#### Risks and Safety:

Oxytocin is a hormone that is secreted by the pituitary gland. The safety of raising OT by a nasal spray has been supported by numerous trials. The doses of OT that will be used in the R21 phase do not exceed the doses that have been used in a number of trials. This study will use a maximum dose of 84 IU administered once whereas studies have administered as much as 320 IU in a single day [1]. [name] (personal communication) has administered 84 IU twice daily and did not find adverse effects. We do not anticipate side effects at this dose although nasal irritation and headache are possible.

Since hyponatremia is a possible effect of OT we will exclude subjects with hyponatremia. Trials of chronic OT in schizophrenia indicate that it may improve symptoms of psychosis. The most serious side effects would occur in pregnant women since OT can increase tone in the pregnant uterus. It can also promote lactation. We will avoid these effects by screening women with pregnancy tests and excluding those who are pregnant.

**Other Possible Oxytocin (intranasal) Risks:** Stinging in the nose, runny nose, or tearing of the eyes. There is also a very small chance (1 report in the scientific literature each) of the development of psychotic thinking. Other possible risks may include: increased heart rate, increased or decreased blood pressure, abnormal heart rate, flushing, headache, allergic reaction that can be severe, and seizure for patients with a history of epilepsy. One of the study psychiatrists will briefly assess each subject before they leave after a study visit to make certain they are not experiencing any ongoing side effects that might require treatment.

**Psychiatric interviews:** It is possible that some of the questions may lead participants to think of upsetting experiences. They may refuse to answer any question they wish, and this will not affect participation.

**Social Cognitive Testing:** These tests may be challenging for participants and may lead to feelings of frustration at times. If a participant tires, they can receive additional rest periods or testing can be continued on another day.

**EEG tasks:** Preparation for application of EEG electrodes involves cleansing the skin with a mild abrasive for the purpose of obtaining a clean, low impedance signal. Participants are informed during preparation that if they feel any discomfort to let the tester know and they will reduce or cease cleansing. Slight flushing where the electrodes were applied to the skin may occur in a very few cases which disappears after a couple of days (similar to receiving a professional facial cleansing).

**Blood draws:** As with any blood draw, there are limited risks of infection, excessive bleeding, nerve injury, blood clots, allergic reaction, nausea, vomiting, dizziness, fainting, or need for blood transfusion.

**Urine Tox Screens:** If a participant tests positive for any illegal drugs, there is a remote possibility that someone outside this research lab may learn of this result, however, the researcher staff will not release this information to anyone and the researchers will obtain a Certificate of Confidentiality, which protects subjects' privacy. Both the urine sample and the results will be identified only by a code number, and the urine sample will be destroyed immediately after the results are obtained.

Although this protocol does not contain procedures that would be expected to increase suicidal ideation or suicide risk, it is not uncommon for patients with schizophrenia to have periods of suicidal ideation. Some of the measurement procedures may identify such suicidal ideation. If suicidal ideation or other evidence of suicide risk is identified during the course of this protocol, one of the clinically trained staff members of this study (i.e., [name]., [name]., Ph.D., [name]., Ph.D., [name]., or [name].) will gather additional information to evaluate lethality and any imminent danger to self and to guide appropriate intervention. Information such as the specific thoughts regarding suicide, any plans to harm oneself, accessibility of means, relevant psychiatric history, use of medications and illicit substances, and availability of support systems will be considered. For lower levels of suicidal ideation, interventions will include notification of the participant's key support persons, such as their treating psychiatrist, psychotherapist, and/or

family members. For imminent suicide risk, hospitalization will be arranged. The limitations on confidentiality regarding disclosures that a participant is having suicidal thoughts are also described in the relevant consent forms.

### **Potential Benefits:**

The R21 may result in a better understanding of the relationship between OT dose and the response of a brain network associated with social information processing. This could result in a more scientific approach to making decisions about the dose of intranasal OT.

### **Risk / Benefit Ratio:**

As discussed previously, there is a great need to develop treatments for social cognitive deficits in patients with psychosis, given their important role in functional recovery. Due to the nature of the study, patients who agree to participate will not derive a lasting benefit from the experimental treatment after the study is complete. However, the knowledge gained from the study will contribute to research which may lead to future improved treatments. Due to the minimal safety risks of the study treatment and procedures, the risks are deemed small and justifiable in relation to the benefits.

**C.1.h. Data Analysis:** The primary goal of the R21 phase is to determine the dose response curve to RT for mu suppression and pupillary response. Prior to modeling the form of the curves we will obtain descriptive statistics and graphical summaries for the measures of target engagement on placebo, at each of the active doses. We will also plot the within subject change scores and the overall dose-response curve. To formally determine whether there is target engagement we will fit a logistic dose response curve to the data for each of the outcome measures. We assume that the OT dose response curve can be adequately modeled using a 4-parameter model with a lower asymptote, slope, E50 (point of half of maximum response), and upper asymptote as the parameters. However, we will also fit a 5 parameter model that allows for an asymmetry in the acceleration and deceleration of the change slope to determine whether the additional parameter is necessary to represent the empirical dose response curve. Independent of which of the models for the dose

response curve we finally choose we will determine whether there is target engagement by testing whether the upper asymptote is significantly different from zero using a z-test based on the parameter estimate and its standard error. Specifically this test allows us to determine whether there is a measurable change in the outcome variable of interest at the optimum dose of OT (where the upper asymptote is reached) while borrowing strength across all the measurement points. For the secondary aim, examining the relationship between target engagement and social salience we will use multiple linear regression models with the social salience measures as the outcomes and change in pupillary response and mu suppression in response (OT vs placebo) as the predictors, adjusted for OT dose.

**Power:** Calculations for the R21 Phase are based on the primary goal of detecting target engagement based on the OT dose response curves for mu suppression and pupillary response using a sample of size  $n=48$ . To estimate power we simulated 10000 replicate data sets following our study design (8 different doses of OT, with 6 observations at each dose) using the effect sizes from our pilot data on pupillary dilation and mu suppression, as well as the results reported in Prehn [31] for 47 normal participants on pupillary dilation, and the results reported in Perry [35] for mu suppression in 24 normal participants.. Specifically, the simulations conservatively assumed that the observed effect sizes represented the upper asymptote (i.e., that the optimal dose had been reached and observations at higher dosage levels than those employed in the respective studies would not show a stronger response). In addition, we assumed that the variances observed at 24, 36, 48, and 60 IU (the middle of the dose range where maximum change in the targets would be expected to occur) were as large as the variances reported in the studies, while the variances at the extreme ends of the range (8, 12, 74 and 84 IU) were half of that. This is based on the patterns of variance heterogeneity common observed for dose response curves.

Under these assumptions the power for detecting a significant upper asymptote is 84% for pupillary response data that show an effect size of  $d = .81$  at the optimal dose, equivalent to the results from our pilot data, and 92% using an effect size of  $d = 1.22$ , the average effect size reported in Prehn [31]. For mu suppression, the power is 89% for an effect size of  $d = 1.03$  at the optimal dose, equivalent to the results in Perry (2010) and 45% for an effect of  $d = .24$ , the average effect seen across task conditions in our pilot data. These are extremely conservative estimates as we expect that these studies were not conducted at the optimal dose, and the estimate of measurement error is most likely inflated as it is based on observations in the steepest part of the dose response curve, where the response is least stable. The wide range of doses that is covered by our design ensures that we will be able to find a stable estimate for the optimal dose of OT.

**C.1.i. Go/No Go decision: After all 48 subjects have completed the OT challenge, we will evaluate** whether the dose response curves for pupillary response or EEG mu suppression show significant target engagement on OT relative to placebo. If there is a significant departure from placebo on either measure of target engagement, the R33 will be initiated.

**D. Milestones and Timeline:** As noted in the timeline, we anticipate that the start-up for the R21 will be accomplished in 3 months. We view this as feasible since all of the assessments – including the target engagement measures – have already been administered in our group. The 2 month start up of the R33 is also feasible since our group therapists are experienced in social cognition training. The rates of subject recruitment required for the R21 and the R33 are similar to recent studies completed by our group.

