#### Specific Aims

**R21 Specific Aims:** This phase will determine the dose-response curve to OT for proposed measures of target engagement (i.e., mu suppression and pupillary dilation). The proposed study will use a single administration, within-subjects, crossover design to model the dose-response to OT across a large range of doses. Subjects with schizophrenia will be randomized to either: 8, 12, 24, 36, 48, 60, 72, or 84 IU OT (6 subjects to each dose). Each subject will receive OT and placebo in administrations separated by one week in randomized order. 30 minutes following OT administration, mu suppression and pupillary response will be assessed. We will also collect data on two measures of social salience (operationally defined here as behavioral tasks of social preference) to examine their correlations with measure of target engagement.

**Aim 1.** To determine the dose-response relationship OT versus placebo for measures of target engagement.

H1: At the optimal level of OT we will observe significant effects on □-suppression.

H2: At the optimal level of OT we will observe significant effects on pupillary dilation.

A Go/No Go decision will be based on Specific Aim 1. If either hypothesis is supported we will decide to go to the R33. Specific Aim 2 is exploratory and the results of the analysis will not be used for a Go/No Go decision.

Aim 2. To evaluate the relationship between target engagement and measures of social salience.

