The inability to use peripheral blood to estimate brain levels of OT has been an important impediment for clinical research with OT. As a result, important decisions for clinical trials, including dose and duration of drug action, have been based on very limited information. This is a substantial problem since studies in animals indicate that the dose-response of OT differs for different behavioral effects with some showing inverted-U shaped dose responses[20]. In addition, it has been difficult to explain why some individuals respond to OT and others do not. The R21 phase of this proposal will evaluate promising indicators of OT's effects on the brain, specifically examining the dose-response relationship for our proposed psychophysiological target measures of neural engagement. If these responses are reliable and valid indicators of OT's brain activity, they have the potential for facilitating treatment development by providing information for dosage selection, duration of drug effects, and identification of non-responders. This proposal will not be able to link OT to a particular receptor – such an approach to target engagement will only be feasible when a PET ligand for the OT receptor is identified. However, our proposed approach can indicate that intranasally administered OT has entered the brain and engaged a social processing network.

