cross and stimulus. Once the choice screen appears they are instructed to identify which stimulus type was shown and they can blink freely. They can then initiate the next trial when they feel they will not need to blink. This task will take approximately 20 minutes to complete.

Pupillary responses from the right eye will be continuously recorded using a ViewPoint EyeTracker USB-220 (Arrington Research, AZ), using an infrared light source and infrared camera. The recording system will be connected to the presentation computer to synchronize trigger signals that indicate the beginning of a trial. Pupillometry data will be continuously recorded at 220 Hz and stored for offline data analysis. Pupillometry data will be analyzed with custom-written scripts in Matlab. Cleaning of data (e.g., removal of blinks) and data reduction will be accomplished following standard procedures [40, 42-44]. Briefly, data will be smoothed using a 20-point moving average filter. Eyeblinks, defined as changes in pupil size that are too large and rapid to represent actual pupil dilation or constriction, will be replaced by linear interpolation. Pupil diameter, measured as the average dilation over the 0.2 s preceding the onset of the stimulus, will be subtracted from pupil diameter after stimulus onset to produce a pupil dilation difference score: positive scores indicate dilation while negative scores indicate constriction. Stimulus-locked pupillary response will be averaged for each stimulus type. Data will be analyzed as the mean change in pupil size occurring between 0.8-2.5 s after stimulus presentation.

**Pilot Data:** Pilot data are available for 8 stable schizophrenia patients on antipsychotic medication who received double-blind 40 IU of intranasal OT or placebo administered a week apart. We assessed the effects of OT on pupillary responses using the paradigm described above. First, we found that greater pupil dilation was seen to faces, compared to a scrambled face (data not shown), consistent with prior studies. Second, as can be seen in Figure 2, OT reduced pupillary dilation to fearful faces in comparison to placebo ( $d=.81$ ), consistent with OT down-regulating amygdala activation to fearful faces [18, 45] and consistent with the one previously published paper showing less dilation on OT to fearful faces [31]. While the sample size is small, these pilot data demonstrate the expected pupillary response to faces and the feasibility of OT to influence pupil size.

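### The Go/No-Go z-test on a freely fitted upper asymptote is unstable and depends on fitting rules the plan does not state; an uncentred contrast test is a cheap and usually stronger replacement

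*Combined protocol and SAP*

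**What the plan says.** Section C.1.h (Data Analysis) fits a 4-parameter logistic curve for each measure. It adds that "we will also fit a 5 parameter model that allows for an asymmetry in the acceleration and deceleration of the change slope", to see whether the fifth parameter is needed. Whichever model is kept, target engagement is decided by "testing whether the upper asymptote is significantly different from zero using a z-test based on the parameter estimate and its standard error". C.1.h identifies this asymptote with the response at the optimum dose.

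Section C.1.i makes the decision on either outcome: "If there is a significant departure from placebo on either measure of target engagement, the R33 will be initiated". In the Specific Aims, H1 and H2 concern the optimal level; H2 reads "At the optimal level of OT we will observe significant effects on pupillary dilation".

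The Power paragraph gives simulated powers in which "the simulations conservatively assumed that the observed effect sizes represented the upper asymptote". They are 84% (d = 0.81) and 92% (d = 1.22) for pupil, and 89% (d = 1.03) and 45% (d = 0.24) for mu suppression.

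None of these sections gives alpha, sidedness, parameter bounds, a rule for boundary or non-converged fits, or a criterion for choosing 4 or 5 parameters. The Power paragraph also omits the true E50, the slope and the SD of the change on the d scale.

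**The concern.** Whether the R33 (N = 120 in Table 4) starts depends on this one statistic, computed for two measures. Three features make it fragile.

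- If OT does nothing, the two asymptotes are equal and the curve is flat for every E50 and slope. Those two parameters are then not identified, and the usual reference distribution for the z-test has no firm basis.
- With six subjects per dose, many fits end on a bound even when there is an effect. The standard error then depends on what the analyst does with that bound.
- It is unclear which end and which sign are tested. Section A.3 notes from animal studies that the dose-response "differs for different behavioral effects with some showing inverted-U shaped dose responses"; under such a shape the high-dose asymptote is not the effect at the optimal dose. Mu suppression is a negative number (C.1.e), and the pilot pupil effect was reduced dilation to fearful faces (C.1.f). Unless signs are reversed, the numerically upper end could therefore be the no-effect end.

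At stake are a false Go, a false No-Go, and an analyst's freedom to choose among fitting rules after seeing the data.

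**Working it through.** **1. The plan's own powers.** With a fixed standard error at two-sided 5%, power = Φ(d/SE − 1.96), so SE = d/(1.96 + Φ⁻¹(power)):

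- d = 0.24: 0.24/(1.96 − 0.126) = 0.131
- d = 0.81: 0.81/(1.96 + 0.994) = 0.274
- d = 1.03: 1.03/(1.96 + 1.227) = 0.323
- d = 1.22: 1.22/(1.96 + 1.405) = 0.363

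No single SE gives all four. The SE of a nonlinear fit need not be constant, so this is no contradiction. With SD 1, slope 4, two-sided 5%, E50 24-48 and the full-Jacobian SE, simulated powers were 12-27%, 59-83%, 63-84% and 63-85%. Of 1,800 combinations of the unstated inputs, two matched all four figures within 2 points. One of them (SD 0.71, E50 36, slope 8, two-sided 10%), rerun with 10,000 replicates, gave 45.9%, 85.2%, 88.5% and 92.0%. The plan's figures are attainable, but only with inputs it does not state.

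**2. Simulation inputs.** From the plan: 8 doses × 6 subjects; upper asymptote = d; full variance at 24-60 IU and half at the four extreme doses. (The Power paragraph lists 74 IU where the design has 72; I used 72, and the two should be reconciled.) Assumed: two-sided 5%, SD of the OT-minus-placebo change 1, E50 24/36/48 IU, slope 2/4/8, lower asymptote 0. Mean change = d/(1 + (E50/dose)^slope). Most cells had 4,000 replicates (error about 1.5 points).

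The main set used nine 4-parameter rules: three ranges of bounds × three SE rules (full Jacobian; parameters at a bound treated as fixed; pseudo-inverse). Further runs used other bounds, two-sided 10%, and the rule that a boundary fit means No-Go.

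**3. Null behaviour and spread.** Under no effect, about 70-99% of 4-parameter fits lay on a bound. Unbounded fitting gave no usable SE in 36-37%.

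| Rule (two-sided 5%) | Null rejection per measure | Power, d = 0.81, E50 36, slope 4 |
|---|---|---|
| Boundary fit = No-Go | about 0.1-1.7% | 11-47% |
| Full SE | 4-6% | 70-78% |
| Bound parameters fixed | 6-10% | 77-87%; 91% with the narrowest bounds |
| All nine rules of the main set | 3.7-15.8% | – |

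At two-sided 10%, null rejection reached 19%. With Go on either of two independent measures, false Go = 1 − (1 − p)²: 0.1% becomes 0.2%, 5% becomes 9.75%, 16% becomes 29%, and 19% becomes 34%.

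**4. Four or five parameters.** The 5-parameter test with full SE, used in every replicate, had about 1% null rejection and about 60% power (d = 0.81, E50 36). AIC or an F-test almost never chose it, leaving the null rate at 4.6%.

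**5. Comparator.** On the same 48 changes y, T = max over shapes c of |Σcy|/√(Σc²y²), with 999 sign-flips. Shapes over 8 to 84 IU: flat (1 throughout); early plateau (.25, .5, 1, 1, 1, 1, 1, 1); late plateau (0, 0, .25, .5, .75, 1, 1, 1); inverted-U (0, .25, .75, 1, 1, .75, .25, 0). Null rejection was 5.1%, and 9.7% for either measure.

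| d | 4-parameter z, nine rules | Contrast | Contrast minus best rule |
|---|---|---|---|
| 0.81 | 53-96% | 78-99.6% | 1-8 points |
| 1.22 | 63-98% | 98-100% | 2-11 points |
| 0.24 | 10-37% | 12-27% | no advantage |

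With the z rules calibrated to a 5% null, the gains are 5-10 points (0.81) and 2-13 points (1.22). At d = 0.24, in the further runs calibrated to 5%, the contrast had 15-28% against 11-26%.

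**6. Why the z-test lags.** With E50 and slope fixed at their true values, power at d = 0.81 was 75-99.9%, against 53-96% with both free. Nor does a larger effect always help: at E50 36, slope 4, full SE and bounds 8-84 IU and 0.5-10, power was 74.4% at d = 0.81 and 74.1% at d = 1.22.

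**7. Where the contrast is not better.** At E50 60 IU and d = 0.81 it had 59-62%, against 66-70% for the best rule; at d = 1.22 it still gained 6-8 points. Contrasts forced to sum to zero had only 28-70% at d = 0.81, so they must be uncentred.

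**8. Inverted-U truth** (peak 36-48 IU, height 0.81). The z-test on the high-dose asymptote had 15-74%, the contrast 73-91% (67-91% without the inverted-U shape). Testing the larger fitted asymptote gave 61-92%, but null rejection of 6-29%.

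**The case against.** The strongest reply is that only the missing rules are a defect and that a new test is a preference. On the plan's own powers, with independent errors, false No-Go is already low: 0.16 × 0.11 = 2% (pupil 0.81, mu 1.03), 0.16 × 0.55 = 9% (both pilot effects) and 0.08 × 0.55 = 4% (pupil 1.22, mu 0.24). Aim 1 concerns dose-response, whereas a flat contrast can reject with no dose trend. This stands in part: the gain over a well-chosen rule is modest. But C.1.i asks only for a departure from placebo, and the plan does not commit to a well-chosen rule.

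Other objections also hold in part. The spread covers the rules I tried, not everything the plan leaves open. The E50 range does not all fit the Power paragraph's plateau assumption. The pupil pilot patients were those "who received double-blind 40 IU of intranasal OT or placebo administered a week apart", and the mu pilot also used 40 IU. At 40 IU the response is 1/(1 + (E50/40)^slope) of plateau: 41/33/19% for E50 48 and 55/60/70% for E50 36 (slopes 2/4/8). Only steep curves at E50 24 come close (89-98%, slopes 4 and 8).

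Four stronger readings are tempting and not supported:

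- That the stated powers are wrong. They can be reproduced, though only with unstated inputs.
- That the contrast always wins. It does not at E50 60 IU and d = 0.81, and at d = 0.24 the ranking depends on alpha, boundary rule and calibration.
- That an inverted-U is expected here. Section A.3 reports it for some behavioural effects in animals, not for EEG or pupil measures in patients.
- That the missing 4- versus 5-parameter criterion does much harm. Under AIC or an F-test it matters little.

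**Conclusion.** The point holds. The decisive test is poorly behaved as a method as well as under-specified: most null fits are on a bound, its error rate depends on unstated rules, and its power need not rise with the effect. Across the rules tried, null rejection per measure was about 0.1-16% at two-sided 5% (up to 19% at 10%), and power at d = 0.81 and E50 36 was about 10-90%.

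For d = 0.81-1.22 and E50 24-48, the uncentred contrast test beat every z rule tried, by about 1-11 points over the best and by far more over a poor one. At d = 0.24 with SD 1 neither test has useful power. If the response is an inverted-U, a z-test on the high-dose asymptote can miss the effect at the optimal dose.

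The curve shapes, SD 1 and alpha are my assumptions, so the absolute powers do not transfer to the plan. The missing rules are a matter of text; the size of the gain is less certain. This should be fixed, and it is cheap to fix.

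**What to change.** For each measure, base Go/No-Go on a pre-specified maximum of uncentred dose-shape contrasts of the OT-minus-placebo change (flat, early plateau, late plateau, inverted-U), each tested against zero. Use a sign-flip reference that follows the randomised visit order, within blocks if order is blocked. State alpha per measure, given that either measure suffices. Keep the fitted curve, with a confidence interval, to describe the dose-response and the effect at the optimal level for H1 and H2. Re-simulate the four powers with alpha, SD, E50 and slope stated.

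If the z-test is kept, state alpha, sidedness, bounds, boundary and non-convergence rules, the model-choice criterion, and the sign and end of the asymptote tested. Calibrate its critical value by simulation under the null.

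Cost: SAP wording and a rerun of the simulations, with no added subjects or measurements. The drawbacks are that the shapes must be fixed in advance, and that a Go then shows a departure from placebo rather than an asymptote or a dose trend.

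### The only formal Aim 1 test does not ask whether response depends on dose: a constant oxytocin effect at all eight doses can pass it

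*Combined protocol and SAP*

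**What the plan says.** Aim 1 (Specific Aims) is "To determine the dose-response relationship OT versus placebo for measures of target engagement". C.1.h repeats it: "The primary goal of the R21 phase is to determine the dose response curve". The opening summary of the protocol adds that the R21 is to establish optimal dosing.

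The hypotheses under Aim 1 are narrower. H2 reads "At the optimal level of OT we will observe significant effects on pupillary dilation", and H1 says the same for mu suppression. The Go rule in C.1.i needs a significant departure from placebo on either measure.

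C.1.h fits a "4-parameter model with a lower asymptote, slope, E50 (point of half of maximum response), and upper asymptote as the parameters". A 5-parameter version is also fitted "to determine whether the additional parameter is necessary to represent the empirical dose response curve". Whichever is kept, target engagement is decided by "testing whether the upper asymptote is significantly different from zero using a z-test". Individual doses are handled descriptively: "we will obtain descriptive statistics and graphical summaries for the measures of target engagement on placebo, at each of the active doses", with plots of within-subject changes and of the overall curve.

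The Power paragraph simulates "8 different doses of OT, with 6 observations at each dose". Its four figures (84%, 92%, 89% and 45%) are all for a significant upper asymptote. It closes by saying that the wide dose range secures a stable estimate of the optimal dose.

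**The concern.** Whether OT differs from placebo at the top of the curve, and whether response changes with dose, are separate questions. The plan tests the first and states its goal in terms of the second. The 4- versus 5-parameter comparison does not close the gap, because it presumes a sigmoid and asks only whether it is symmetric. The Aim 2 regression only adjusts for dose.

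A trial in which every dose had the same effect could therefore pass the test and be written up with a fitted sigmoid, an E50 and an optimum, although the data did not distinguish the doses. Subjects are randomised to eight doses in order to learn about dose, so the planned analysis should be able to say whether that was achieved.

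**Working it through.** **1. What the test can and cannot see.** Write the 4-parameter curve for the OT-minus-placebo change as f(x) = L + (U − L) / (1 + exp(−k(x − E50))). The planned null hypothesis is U = 0. No dose dependence is U = L. If U = L = c with c ≠ 0, then f(x) = c at every dose whatever E50 and k are. The planned null is false, dose is irrelevant, and E50 and k are not identified.

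**2. The plan's own power.** The documents give the design (8 × 6 = 48), the effect sizes and the variance pattern (full at 24–60 IU, half at the extremes). They do not give E50, slope, alpha, sidedness or fitting constraints. Assumed here: E50 of 18, 24 or 42 IU; slope 0.1 or 0.2 per IU; two-sided 5%; d on the scale of the change-score SD. Bounded 4-parameter fits, 150–400 replicates per setting (simulation error about 2–4 points):

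| d | Stated power | Simulated |
|---|---|---|
| 0.81 | 84% | 83–91% |
| 1.03 | 89% | 82–92% |
| 1.22 | 92% | 77–95% |
| 0.24 | 45% | 20–30% |

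The first three stated values lie within the simulated ranges. The 45% was not matched by any fit tried. The simple one-sample formula gives 0.24 × √48 = 1.66, so power is Φ(1.66 − 1.96) = 38% two-sided, or Φ(1.66 − 1.645) = 51% one-sided. The present point does not depend on that figure.

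**3. Flat truth.** Same mean d at all eight doses, SD 1. Percentage of trials passing |U/SE| > 1.96, with two tests of dose differences on the same data:

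| Flat d | 4-par. bounded | 4-par. unbounded | 4-par. log dose, bounded | L fixed at 0 | F test (7, 40 df) | Linear trend |
|---|---|---|---|---|---|---|
| 0.24 | 19 | 15 | 18 | 18 | 6 | 7 |
| 0.5 | 52 | 36 | 55 | 26 | 4 | 4 |
| 0.81 | 77 | 46 | 73 | 17 | 4 | 5 |
| 1.22 | 82 | 57 | 80 | 9 | 5 | 6 |

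A separate run of the bounded fit gave 25%, 53% and 72% at d = 0.3, 0.5 and 0.81. With the plan's variance pattern at d = 0.81, the three 4-parameter fits passed 87%, 53% and 82%. Under the bounded fit, a flat d = 0.81 (77–87%) thus passes nearly as often as a true sigmoid of that size (83–91%).

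Under the flat truth at d = 0.81 the bounded fit's E50 had median 36 IU and 5th–95th percentiles of about 8–83 IU, which is the whole tested range. In further runs at d = 0.3–0.81, 65–88% of flat trials that passed had E50 inside 8–84 IU. Of the unbounded fits, 15–20% did not converge.

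**4. Power to detect dose dependence.** Worked case: linear trend, d = 0.81, E50 24 IU, slope 0.1, equal SD 1. The doses average 344/8 = 43 IU, with sum of squared deviations 5,432. The sum of (dose − 43) × mean response is 50.9. The noncentrality is 6 × 50.9 / √(6 × 5,432) = 305.4 / 180.5 = 1.69, which gives 38% power. With E50 42 IU the same steps give 54% (slope 0.1) and 64% (slope 0.2). The 7-df F test gives 18–33% over these three curves.

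A centred maximum-contrast test at d = 0.81 with E50 24–36 IU gave 36–49% with equal variances and 50–62% with the plan's halved end variances. With E50 12 IU it gave 28–35%. A further check spanned about 23–63%. Rounded, this is 20–65% for E50 of 12–36 IU.

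**5. Non-monotone truth.** Section A.3 notes inverted-U responses for some OT effects in animals. For bell-shaped truths peaking at 36–48 IU with d = 0.81, linear trend had 5–10% power. A maximum-contrast test limited to monotone shapes had 12–23%.

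**The case against.** The strongest reply is that the z-test does what H1, H2 and the Go rule ask. Determining a curve can be read as estimation, and with six subjects per dose, estimating rather than testing is defensible. This stands, and it is why the Go rule is not challenged. It does not cover the assurance about the optimal dose, for which the plan promises neither a test nor an interval.

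A reader might go on to infer several stronger things that the documents do not support:

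- *That nothing would reveal a flat response.* Summaries at each dose and plots of the changes and the curve are planned, and a flat pattern could be seen in them. They are informal, with no rule attached.
- *That the R33 dose would be read off a meaningless E50.* The plan places the optimum where the upper asymptote is reached, not at E50. It gives no dose-selection rule, and the R33 needs a new IRB submission.
- *That a flat response always passes and always yields an E50.* The pass rate depends on unstated fitting choices. It is 9–26% at d = 0.5–1.22 if the lower asymptote is fixed at zero, although C.1.h lists that asymptote as a parameter. Some unbounded fits do not converge.
- *That half of Go decisions would lack evidence that dose matters.* Across the runs at d = 0.81 this share ranged from 29% to 79%, according to the assumed E50, slope and variances. No single value can be defended.

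**Conclusion.** The concern holds as a gap between the stated goal and the planned inference. The upper-asymptote test is valid for target engagement but is not evidence of dose dependence. That follows from the model and needs no simulation.

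The size does rest on assumptions: roughly 25–75% of flat-response trials pass at d = 0.3–0.81 with a bounded 4-parameter fit, and fewer at the larger effects under the two alternatives. Against that, power to show that dose matters is only about 20–65% at d = 0.81, the plan's own pilot effect for pupil response. The claim that the design secures a stable estimate of the optimal dose is therefore not a property this plan has. The Go decision as defined is unaffected.

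**What to change.** Leave the Go rule unchanged.

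1. **Test.** In C.1.h, pre-specify for each measure one two-sided 5% test of dose dependence across the eight randomised groups. Use a centred maximum-contrast test whose candidates include several monotone logistic shapes and at least one inverted-U. A monotone-only set would usually miss the pattern raised in A.3.
2. **Intervals.** Report a confidence interval for E50 and for the estimated dose at which the upper asymptote is reached. Define the latter in advance, because a logistic curve only approaches its asymptote. State the fitting constraints.
3. **Reporting rule.** If the upper-asymptote test is positive and the dose test is not, report that OT differs from placebo and that the tested doses were not distinguished. Say that this is not evidence of no dose effect, and label any optimum as exploratory.
4. **Power paragraph.** Replace the assurance about the optimal dose. Beside the present figures, give the power for dose dependence as a range with its assumed E50, slope and variances.

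The cost is one extra test per measure and a few lines of text, with no new subjects or data. The trial may have to report that doses were not distinguished, the stated power for Aim 1 will look less favourable, and the inverted-U contrast costs a few points of power if the curve is monotone.
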